## 3 Rationale and Objective

### 3.1 General Design

PKC412 (midostaurin) is known to inhibit the c-KIT RTK activity [22] as well as the FLT3 kinase, both in patients with ITD and TKD mutations. It should therefore be possible to abrogate the negative impact of pathologically increased c-KIT or FLT3-ITD activity on relapse and overall survival by using midostaurin in this patient population. Aim of the proposed clinical trial is to prove the efficacy of midostaurin in c-KIT or FLT3-ITD mutated t(8;21) AMLs.

### 3.2 Choice of Chemotherapy Regimen

For patients with newly diagnosed AML under 60 years of age, the proposed standard chemotherapy induction regimen is 7+3 cytarabine in combination with antracylins or mitoxantrone. In this trial, all patients with no signs of progression of primary refractory disease after first standard induction treatment as assessed by early bone marrow assessment on day 14-16, will receive a second cycle of induction with daunorubicine and cytarabine (DA 7+3). Consolidation treatment with at least three cycles of high-dose cytarabine (HiDAC) is the current international standard in patients with favourable or intermediate cytogenetic profile [23]. General acceptance of usage of this regimen as the standard for AML chemotherapy in this population predates FDA or European Health Authority approval.

### 3.3 Choice of PKC412 Regimen

We have chosen to administer PKC412 at 50 mg bid as per the sequential regimen. The choice of the sequential regimen, rather than simultaneous regimen of PKC412 was based on the following considerations: In vitro data suggests that although additive and/or synergistic cytotoxic effects are observed when FLT3 inhibitors are given simultaneously, or after chemotherapy (chemo  $\Rightarrow$  PKC412), exposure of cells to FLT3 inhibitors before chemotherapy (PKC412  $\Rightarrow$  chemo) has antagonistic effects on cytotoxicity [24]. Thus the simultaneous regimen would translate into one mimicking an antagonistic interaction, particularly as relates to the effect of earlier doses (e.g. days 1-3) of PKC412 on later doses of cytarabine (e.g. days 4-7).

Recently, data have been published indicating a FLT3-ligand mediated reduction in efficacy of tyrosin-kinase inhibitors when given after chemotherapy instead of parallel to chemotherapy [25]. However, in study 2106, the tolerability of a combined regimen was low with patients mainly suffering from nausea and vomiting, leading to the selection of a sequential application of chemotherapy followed by midostaurin. Furthermore, the results by Sato et al. are derived from in-vitro models and have not been confirmed in a clinical setting yet. Finally, the findings on the influence of tyroskinkinase-receptor ligands on inhibitory efficacy seem to be specific for FLT3 while ligand levels seem to be independent from chemotherapy in the case of the KIT molecule ([name], personal communication). Since the incidence of c-KIT mutations in t(8;21) AML is much higher than the incidence of FLT3-ITD, the main number of patients will be diagnosed with c-KIT*mut* rather than FLT3-ITD. Considering all arguments, the investigators of this trial have decided to apply the sequential dosing schedule of midostaurin as used in study CALGB 10603/CTSU C10603 (RATIFY).

The MIDOKIT study design also includes a continuous maintenance phase of single agent PKC412 at 50 mg bid for up to an additional 12 months. Standard therapy of adults with AML does not routinely involve a maintenance phase of chemotherapy after completion of consolidation. However, data in the literature [MRD w/FTL3] suggest that minimal residual disease that can be detected in AML patients with FLT3 mutation predicts rapid relapse once chemotherapy is completed. Thus the continued administration of an oral, non-cytotoxic and well-tolerated drug such as PKC412 post chemotherapy might continue to inhibit growth or even kill residual FLT3 mutated blasts present at the end of a routine course of chemotherapy to prolong survival has recently been demonstrated in newly diagnosed Ph+ALL patients. Patient survival is significantly improved compared to historical controls when the anti-bcr/abl drug Glivec/Gleevec is given to Ph+ALL patients throughout therapy, from induction to relapse, including a maintenance phase with Glivec alone post completion of chemotherapy [26].

# 4 Study Plan

## 4.1 Study Design

This study is planned as a pilot phase-IIa study for the assessment of efficacy and safety. The trial is a one-arm open-label multicentre study.

## 4.2 Timetable

Enrolment of first subject (FPFV)*:	1 May 2012
Enrolment of last subject:	30 April 2016
End of trial of last subject (LPLV)*:	31 May 2018
Closing of database:	31 July 2018
Completion of statistical analysis:	01 August 2018
Integrated final report:	30 September 2018
Duration of treatment per subject:	16 months
Planned duration of follow-up	9 months
Planned interim analysis or analyses:	none

\*Normally, the start/end of the study is defined as the first/last visit of the first/last subject.

## 4.3 Study Treatment

This is a one-arm open-label study, i.e. all included patients will receive the same treatment:

Patients with non-refractory chemo-responsive disease after one cycle of standard 7+3 induction treatment will enter the study before commencing second induction treatment. Standard induction treatment is defined as a seven-day continuous infusion of 100-200 mg/m^2/d plus three doses of daunorubicine, or idarubicine, or mitoxantrone. Chemo-responsive non-refractory disease is defined by reduction of blast count and/or cellularity on the early bone marrow assessment on day 14-16 of the first induction treatment and peripheral blast clearance, i.e. the absence of myeloid blasts in peripheral blood on day 14-16 of the first induction treatment. The first cycle of induction treatment after initial diagnosis is not part of this trial.

After inclusion in the study, patients will receive one cycle of standard DA (days 1-7) in combination with midostaurin treatment (days 8-21). After confirmation of responsive disease and complete remission, patients will continue with three cycles of high-dose cytarabine (HiDAC, days 1, 3, 5) in combination with midostaurin (days 8-21), which shall be administered depending on adequate blood counts and sufficient organ function. After a minimum of 14 days after the last midostaurin application in the last cycle of MidoHiDAC, i.e. earliest on day 36 after the beginning of the last cycle of MidoHiDAC, patients shall commence maintenance treatment. Maintenance treatment consists of 12 cycles with 28 days per cycle, i.e. continuous midostaurin application for a total of 336 days. After a maximum of 12 cycles midostaurin maintenance, patients will be followed up for additional 9 months. If patients stop study treatment or maintenance prematurely, i.e. before having completed 12 cycles of midostaurin maintenance, patients will be followed up until 25 months after study entry.

### For details, see section 7

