	survival (OS), Relapse-free survival	(RFS), morphologic and molecular				
	CR rate, incidence of AEs/SAEs, MR	D kinetics				
TIMETABLE	Enrolment of first subject (FPFV)*:	1 May 2012				
	Enrolment of last subject:	30 April 2016				
	End of trial for last subject (LPLV)*:	31 May 2018				
	Closing of database	31 July 2018				
	Conclusion of statistical evaluation:	1 August 2018				
	Integrated final report:	30 September 2018				
	Treatment duration per subject: 16 months					
	Estimated duration of follow-up 9 months					
	Study duration per subject 25 months					
	Planned interim analysis: none					
	*Study begin/end is generally the first/last visit of the first/last subject					
SAMPLE SIZE	n = 18 patients					
	midostaurin 50 mg (two 25 mg capsu	ules) is given in combination with the				
	second of two induction cycles and	in combination with three cycles of				
	gh-dose cytarabine (HiDAC) consolidation chemotherapies and					
	maintenance treatment in patients w	vith c-kit or FLT3-ITD positive t(8;21)				
	part of the study	gn. The first cycle of induction is not				
	Second cycle of induction chemotherapy (7+3 scheme).					
	Cytarabine 100 mg/m  days 1-7					
	Daunorubicin 60 mg/m  days 3-5					
	Midostaurin 50 mg (2 capsules) twice	e daily days 8-21				
	Triple consolidation chemotherapy:					
	Cytarabine 3000 mg/m  twice daily d	ays 1, 3, 5				
	Midostaurin 50 mg (2 capsules) twice daily days 8-21					

	Maintenance treatment:				
	Midostaurin 50 mg (2 capsules) twice daily continuously for 12 months				
Main Inclusion Criteria	
 
Diagnosis of c-KIT mutated t(8;21) AML i.e.
 
>20% myeloid blasts in bone marrow and/or peripheral blood at initial diagnosis
 
Plus cytogenetic diagnosis of aberration t(8;21)/AML1-ETO
 
Plus mutation of c-KIT gene (mut-KIT17 or mut-KIT8) or FLT3-ITD mutation or both c-KIT and FLT3-ITD mutations
 
Chemoresponsive disease as determined by early bone marrow assessment on day 14-16 after first cycle of induction therapy with cytarabine in combination with daunorubicine or idarubicine, or mitoxantrone
 
Fit for further intensive chemotherapy
 
Age 18-65 years
 
ECOG performance status of 0-2
 
Life expectancy of at least 12 weeks
 
[Exact list of inclusion criteria is specified in section 5.3]
 
				

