#### **Consolidation treatment: MidoHiDAC**

Each consolidation cycle is four weeks in duration, and should begin within two weeks following hematologic recovery (ANC  $\geq$  1000/µL and platelet count  $\geq$  50.000/µL), but not sooner than four weeks from the beginning of the previous cycle. If a consolidation cycle is delayed >8 weeks from

the start of the previous course of induction or consolidation due to slow resolution of toxicity or slow recovery of complete blood counts (CBC), please contact the SAL central study office.

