### Midostaurin maintenance

Patients who continue in complete remission (by bone marrow aspiration and blood evaluation) after three cycles of consolidation therapy will receive midostaurin maintenance therapy. If, in the opinion of the investigator, the clinical condition of a patient does not allow a third cycle of MidoHiDAC, the SAL central study office should be contacted for medical advise. If the LKP agrees that the risk of serious adverse events is too high in case of a third MidoHiDAC application, midostaurin maintenance may commence after two cycles of MidoHiDAC.

Prior to initiation of midostaurin maintenance therapy, all significant acute toxicity from consolidation therapy must have resolved to grade 2. Maintenance will begin after hematologic recovery (ANC  $\geq$  1000/ µL, platelet count  $\geq$ 50,000/µL) from remission consolidation and no sooner than 14 days after the last midostaurin application in the last cycle of MidoHiDAC, i.e. earliest on day 36 after the beginning of the last cycle of MidoHiDAC. Maintenance treatment must be started before day 64 after the beginning of the last cycle of MidoHiDAC, i.e. patients who cannot start maintenance treatment until 64 days after the beginning of the last cycle of MidoHiDAC, i.e. patients who cannot start maintenance treatment until 64 days after the beginning of the last cycle of MidoHiDAC, i.e. patients who cannot start maintenance treatment until 64 days after the beginning of the last cycle of the last cycle of MidoHiDAC will stop study treatment and will be followed up until 25 months after study entry.

Maintenance treatment consists of continuous midostaurin application for 12 cycles with 28 days per cycle:

Midostaurin50 mg (2 capsules) p.o. twice dailydays 1-28Start of new maintenance cycle on day 29

Midostaurin 50 mg (two 25 mg capsules) is given twice a day by mouth on days 1-28. Patients should take their doses at approximately the same time each day, and approximately 12 hours should elapse between the morning and evening doses. Each daily dose should be given with food and a glass of water (approx. 240 ml). Patients should be instructed to swallow capsules whole and not chew capsules. If vomiting occurs, no re-dosing is allowed before the next scheduled dose.

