For **remission assessment**, a bone marrow aspirate (or bone marrow biopsy) must be performed every three months during maintenance treatment and during follow up including the end-of-study visit 9 months after the end of the 12-month-maintenance period or 25 months after study entry in case of premature discontinuation of study treatment. At each bone marrow aspiration, material should be obtained and sent to the central SAL laboratory in Dresden for MRD diagnostics (see section 7.4).

A suspected relapse during the entire study duration must be confirmed by bone marrow aspiration or biopsy.

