## 13.2 Target Variable/Endpoints

## 13.2.1 Primary Target Variable

As pointed out in section 2.1, the reduction of overall survival in patients with c-KITmut is mainly due to a higher incidence of relapses while in FLT3-ITD patients, primary resistant disease leads to the inferior prognosis during the early course of the disease. Since the patient group in this trial consists both of c-KITmut and FLT3-ITD patients, event-free survival seems to be the measure to capture both early treatment failure in FLT3-ITD and later relapse from CR in c-KITmut patients. Therefore, the primary study endpoint will be event-free survival (EFS).

Event-free survival rate at 2 years is defined as the time from study inclusion (date of informed consent) until either primary treatment failure or hematologic relapse or death from any cause occurs. Primary treatment failure is defined as the absence of CR/CRi five weeks (35 days) after the start of MidoDA induction treatment.

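### Follow-up of patients who complete maintenance runs from the end of maintenance, not from study entry, so their 2-year EFS status is not guaranteed, mainly on the permitted two-consolidation path

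*Protocol*

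**What the plan says.** **Endpoint.** Section 13.2.1 starts the EFS clock at consent: "Event-free survival rate at 2 years is defined as the time from study inclusion (date of informed consent) until either primary treatment failure", relapse or death. Section 13.3 analyses a binary status at 2 years and rejects the null hypothesis if at least 13 of 18 patients are event-free.

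**Follow-up.** Sections 4.3 and 7.1 use two different anchors.
- Completers are followed from the end of maintenance: "After a maximum of 12 cycles midostaurin maintenance, patients will be followed up for additional 9 months". Section 7.1 places "the end-of-study visit 9 months after the end of the 12-month-maintenance period".
- Early stoppers are followed from entry. If they stop "before having completed 12 cycles of midostaurin maintenance, patients will be followed up until 25 months after study entry".

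Section 10.1.2 ends a subject's participation at the end-of-study visit. The Synopsis gives "Study duration per subject 25 months", made up of 16 months of treatment and 9 months of follow-up.

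**Schedule.** Section 4.3 says: "Maintenance treatment consists of 12 cycles with 28 days per cycle, i.e. continuous midostaurin application for a total of 336 days". The Synopsis and the remission-assessment text in section 7.1 call the same period 12 months. A consolidation cycle starts after recovery, "but not sooner than four weeks from the beginning of the previous cycle". Maintenance starts on day 36 of the last consolidation cycle at the earliest and before day 64. If a third cycle is judged too risky and the coordinating investigator agrees, "midostaurin maintenance may commence after two cycles of MidoHiDAC".

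**Missing status.** Section 13.4 excludes patients whose 2-year status cannot be evaluated from the primary analysis. It adds best-case and worst-case sensitivity analyses.

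**The concern.** The 25-month duration covers the 2-year endpoint only if treatment really takes 16 months. The cycle rules do not ensure that, and nothing sets a minimum follow-up from entry for completers. The result is odd: a patient who stops during the twelfth maintenance cycle is followed to 25 months, while one who finishes that cycle may leave the study at about 23 months.

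The loss also runs one way. A patient with an event has a known status, and an early stopper is followed past 2 years. Only a patient who completes maintenance event-free can lose the 2-year status through this rule, and that patient is a likely success. With 18 patients and a threshold of 13, removing one success can reverse the conclusion.

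**Working it through.** **1. The plan's own design reproduces.** For X ~ Bin(18, p), P(X ≥ 13 | 0.5) = 0.0481 and P(X ≥ 13 | 0.8) = 0.867. Eighteen is the smallest sample size with one-sided alpha at most 0.05 and power at least 0.80; n = 16 gives power 0.798 and n = 17 gives 0.758.

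**2. Time of the completer's last visit.** Count days from day 1 of MidoDA:

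last visit = (number of consolidations × cycle interval) + days from the start of the last consolidation to maintenance + 335 (first to last of 336 maintenance days) + 274 (9 months)

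Inputs: a cycle interval of at least 28 days (section 7.1); earliest maintenance start 35 days and latest 62 days after day 1 of the last cycle (sections 4.3 and 7.1). Interruptions are taken not to prolong maintenance, since missed doses are not made up (section 7.2.1). Two years is 730 days.

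| Consolidations | Interval | Maintenance start | Sum | Last visit | Against 730 |
|---|---|---|---|---|---|
| 2 | 28 | earliest | 56 + 35 + 335 + 274 | 700 | 30 short |
| 2 | 35 | earliest | 70 + 35 + 335 + 274 | 714 | 16 short |
| 2 | 42 | earliest | 84 + 35 + 335 + 274 | 728 | 2 short |
| 2 | 28 | latest | 56 + 62 + 335 + 274 | 727 | 3 short |
| 2 | 35 | latest | 70 + 62 + 335 + 274 | 741 | 11 beyond |
| 3 | 28 | earliest | 84 + 35 + 335 + 274 | 728 | 2 short |
| 3 | 35 | earliest | 105 + 35 + 335 + 274 | 749 | 19 beyond |

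**3. Calendar dates and the consent clock.** EFS runs from consent, so any gap between consent and MidoDA adds to follow-up. The protocol does not fix that gap; 0 and 7 days are assumed. Over entry dates from May 2012 to April 2016, with the earliest maintenance start:
- Two consolidations, 28-day cycles: 28 to 32 days short with no gap, 21 to 25 days short with a 7-day gap.
- Two consolidations, 35-day cycles: 14 to 18 days short with no gap, 7 to 11 days short with a 7-day gap.
- Three consolidations, 28-day cycles: 0 to 4 days short with no gap, 3 to 7 days beyond with a 7-day gap.

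**4. Break-even.** The two-consolidation path has three intervals: MidoDA to the first consolidation, first to second, and second to maintenance. They must average (730.5 − 336 − 274) / 3 = 40.2 days; the permitted minimum is (28 + 28 + 35) / 3 = 30.3. The three-consolidation path has four intervals, which must average (730.5 − 336 − 274) / 4 = 30.1 days; the minimum is (28 + 28 + 28 + 35) / 4 = 29.75.

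**5. Why the nominal 25 months does not hold.** 336 / 30.44 = 11.0 months. Minimum treatment is therefore 14.0 months with two consolidations and 14.9 months with three, not 16.

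**6. Effect of losing one success.** 13/18 has one-sided p = 0.048 and an exact lower 95% bound of 0.502, above 0.5. With one event-free patient excluded, 12/17 has p = 0.072 and a lower bound of 0.478, below 0.5.

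**7. Illustration of power.** Suppose each success is non-evaluable with probability q. The expected observed rate is 0.8(1 − q) / (1 − 0.8q). Power sums over s successes in 18 and k of them lost, rejecting when s − k reaches the exact 5% threshold for 18 − k patients (13 for 18, 13 for 17, 12 for 16). No value of q is given in the protocol.

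| Assumed q | Expected rate | Power |
|---|---|---|
| 0 | 0.80 | 0.867 |
| 5% | 0.79 | 0.79 |
| 10% | 0.78 | 0.72 |
| 20% | 0.76 | 0.59 |

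**The case against.** The minimum intervals are a floor. Consolidation waits for confirmed remission and blood-count recovery, and only a delay beyond 8 weeks prompts contact with the study office. Two-consolidation maintenance is an exception for patients not fit for a third cycle, who may well recover slowly. The intent is clear: 25 months per subject, and a last visit of 31 May 2018, 25 months after the last planned enrolment. Section 13.4 sets no assessment window, and an SAP could accept a remission documented a few days early. The sensitivity analyses would also include any excluded patient.

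Much of this stands, and it rules out three readings that someone might take from the figures.
- **That completers in general are lost.** On the planned path the shortfall is at most about 4 days, and a week between consent and treatment or a small cycle delay removes it.
- **That 727 days is a ceiling for two consolidations.** It holds only with 28-day chemotherapy intervals. With 56-day intervals and the latest maintenance start, the last visit is at 56 + 56 + 62 + 335 + 274 = 783 days.
- **That power falls to 0.72 or any other stated value.** The loss rates are assumptions, and zero loss is possible.

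The objection does not remove the gap on the two-consolidation path, which persists with 35-day cycles and the earliest maintenance start. A window of a few days would not cover 16 to 30 days, and an SAP cannot supply data from after participation has ended. The sensitivity analyses show the problem but leave the primary decision unchanged.

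**Conclusion.** The point holds in limited form. The protocol requires a 2-year status but does not guarantee follow-up to 2 years for patients who complete maintenance. The material shortfall, up to about one month, is confined to the two-consolidation path when its three intervals average less than about 40 days. Any resulting exclusion removes a likely success, so the bias is downward and against the treatment. In a trial of 18, one exclusion can decide the result, although the 13/18 example is by construction the borderline case.

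The conclusion assumes that interruptions do not prolong maintenance, that the gap from consent to MidoDA is 0 to 7 days, and that a last visit before 24 months leaves the status not evaluable under section 13.4. The number of patients affected cannot be derived from the protocol.

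**What to change.** In sections 4.3 and 7.1 and in the visit schedule, follow all patients until 9 months after the end of maintenance or 25 months after study entry, whichever is later. Require a status and marrow assessment at or after 24 months from informed consent.

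The wording whichever is later matters. A flat 25-month rule (about 761 days) would shorten follow-up for slower patients. Three consolidations at 56-day intervals with the latest maintenance start run to 168 + 62 + 335 + 274 = 839 days, so about 78 days would be lost.

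Separately, the places that give maintenance as 12 months and as 336 days must be reconciled; which is intended is for the sponsor to state.

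The cost is protocol wording and a later final visit for some completers, by up to about two months (761 − 700 = 61 days). The sample size of 18, the threshold of 13, alpha 0.0481 and power 0.867 are unchanged, and 25 months after the last planned enrolment already fits the timetable.

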## Flow Diagram Study Treatment

### 4.4 Participating Centres

25 centres are planned in Germany, which must meet the structural and personnel requirements for performing the planned regular study-related investigations. If necessary, additional qualified centres can be included in the performance of the study.

### 4.5 Number of Study Participants

18 subjects will be enrolled in the study

## 5 Subject Population and Selection Criteria

### 5.1 Target Population / Main Diagnosis

Patients diagnosed with a c-KIT and/or FLT3-ITD t(8;21) AML with documented response to standard cytarabine based induction treatment will be treated in this trial.

